22.2 SAMPLE SIZE ASSUMPTIONS AND CALCULATIONS

The sample size calculation is based on data from Brunoni et al (2017). The calculation is based on a two- sample t-test for mean difference with the following assumptions:

- Group difference in means = 3.2
- Standard deviation of Investigational and Sham groups = 7.1 and 7.9, respectively
- One-sided type I error = 0.025
- 80% power

The resulting sample size is 176 subjects. To obtain an increase in statistical power (87.6%), 216 subjects were chosen. Accounting for 20% attrition, the overall sample size will be 270 subjects.

22.3 STUDY POPULATIONS

22.3.1 INTENT-TO-TREAT ANALYSIS SET (ITT)

All randomized subjects will be included in the "intent-to-treat" (ITT) analysis set and classified according to their intended treatment regardless of failure to complete the required follow-up examinations. Subjects excluded prior to randomization will be considered screening failures.

22.3.2 As TREATED ANALYSIS SET (AT)

The As Treated Analysis Set (AT) will consist of ITT subjects who receive at least 1 treatment of study device (Active or Sham). Subjects will be analyzed according to the study treatment received. The As Treated Analysis Set will be used for all summaries of safety and tolerability data.

22.3.3 MODIFIED INTENT-TO-TREAT ANALYSIS SET (MITT)

The modified intent-to-treat (mITT) analysis set will include ITT subjects who receive at least 1 treatment of study device (Active or Sham) and will exclude patients who were randomized in error. The number of exclusions from the mITT analysis set is expected to be small and will only be

based on information that was known or could have been known prior to the first treatment. Subjects in the mITT population will be analyzed in the group to which they were randomized.

22.3.4 PER PROTOCOL ANALYSIS SET (PP)

The Per Protocol (PP) analysis set will be comprised of the following:

- Subjects in the mITT analysis set
- Subjects with device failure within the 10-week follow-up period
- Subjects with deviation from the clinical investigation plan is caused by the investigational device or by problems with respect to tolerability

Subjects who will be excluded from the PP analysis set are as follows:

- Subjects with major protocol violations that would be expected to confound clinical assessment during follow-up as determined by the PIs.
- Subjects who took new pharmaceutical substances or treatments during the clinical investigation which are listed as an exclusion criteria;
- Subjects who do not meet the inclusion criteria or exclusion criteria.
- Users who have performed less than 10 sessions (300 minutes) during the first 3 weeks will be excluded from the analysis.

Subjects in the PP population will be analyzed in the group to which they were randomized.

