7 SCHEDULE OF PROCEDURES

Table 1. Schedule of Procedures. Activities in blue cells are performed by trained graduate researchers supervised by a trained psychiatrist, and red cells are to be completed by the participant.

	Pre-Treatme nt		E	Blinded Pha	ise		Open-La Phas	abel e	Early termination ⁸
Activity	Week -3 to -1 (± 3 days)	Week 0	Week 1 (± 3 days)	Week 4 (± 3 days)	Week 7 (± 3 days)	Week 10 (± 3 days) Final blinded visit ¹	Week 10 (± 3 days) Open Label Start	Wee k 20 (± 3 days)	Week 1-20
Informed Consent	х								
Screening and baseline Video Call	х								
Diagnostic Assessment for MDD	X٩								
Intervention Kit Shipped to subject	X ⁵								
Randomization ⁶		Х							
Technical onboarding		х							
Initial Visit		Х							
Video call	Х	Х	Х	Х	Х	Х		Х	Х
MINI	Х								
HDRS-17	X		X	Х	X	X		X	X
MADRS	Х		Х	Х	Х	Х		X	Х
MADRS-s	X	X ⁴	X	X	X	X		X	Х
C-SSRS	X		X X	X X	X X	X		X	X X
YMRS	X X		X	X	X	X X		X	X
HAM-A	X					X		X X	X
EQ-5D-3L RAVLT	X					X		X	X
SDMT	~	X ²				 X ²		Λ X ²	^
TAQ	X	~				X		X	Х
AEQ						X		X	X
Healthcare Visit Survey ³						X		X	X
FLOW FL-100 use ⁷		х	х	х	х	х	х	Х	
Record/Review Concomitant Medications	х	х	х	х	х	х		х	х
Record/Review Adverse Events		Х	Х	Х	Х	Х		Х	Х

CA-127-T1, v3.0 Flow Neuroscience AB, FL001 CONFIDENTIAL Page **19** of **69**

¹ The week 10 visit includes the study Primary end-point. This will be the final blinded visit and will be the start of the open label phase of the study. Participants in the Sham arm will be informed of their assignment and will restart with active stimulation for 10 weeks; participants in the Flow FL-100 arm will be allowed to continue maintenance treatment for 10 more weeks at 3 sessions per week. The unblinding will occur after the primary end-point data has been recorded. ² Optional

³ Participants will be surveyed about the number of times he/she has sought healthcare due to depression during the previous 10 weeks.

⁴ Participants will be required to answer the nine questions of the MADRS-s form in the app to start the first stimulation session during the technical onboarding.

⁵ Participants will be required to start treatment within 24 days from completing the baseline surveys.

⁶ Completed after eligibility is confirmed by the investigator; when the participant signs up with their email in the trial app they will automatically be randomized to the sham or active treatment arm (with 50% probability).

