11.1 STUDY DURATION

The study is expected to take approximately 10 months from first participant enrolled to the last open-label visit.

- 5 months enrollment period (estimation)
- 5 months treatment and open-label

The follow-up period during the clinical investigation shall permit the demonstration of performance over a period, sufficient to represent a realistic test of the performance of the investigational device and allow any risks associated with adverse device effects over that period to be identified and assessed.

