11.2 TREATMENT/CONTROL GROUPS

For each participant, the trial will be conducted in 2 phases: blinded and open label.

Figure 5 Participant Activity Flowchart

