13.9 STUDY COMPLETION/DISCONTINUATION

The Primary Endpoints will be evaluated at 10 weeks. Participants will complete study participation at 10 weeks unless consented and enrolled in an additional 10-week open-label portion of the study. Participants enrolled in the open-label phase will complete the trial after 20-weeks.

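### The per-protocol exclusion for newly started excluded treatments has no time limit, so events after Week 10 and after unblinding can remove valid Week 10 data from that set

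*Protocol*

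**What the plan says.** Protocol 22.3.4 starts the PP set from mITT and then lists exclusions. One of them removes "Subjects who took new pharmaceutical substances or treatments during the clinical investigation which are listed as an exclusion criteria". No week is attached.

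Two other bullets in the same section do carry a window: "Subjects with device failure within the 10-week follow-up period" and "Users who have performed less than 10 sessions (300 minutes) during the first 3 weeks will be excluded from the analysis".

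The investigation runs past Week 10 for anyone who continues:

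- Protocol 11.2: "For each participant, the trial will be conducted in 2 phases: blinded and open label".
- Protocol 11.1: "The study is expected to take approximately 10 months from first participant enrolled to the last open-label visit".
- Protocol 13.9: "Participants will complete study participation at 10 weeks unless consented and enrolled in an additional 10-week open-label portion of the study". It then adds: "Participants enrolled in the open-label phase will complete the trial after 20-weeks".

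Table 1, footnote 1 (Protocol section 7) places unblinding after the Week 10 endpoint data are recorded, and says: "Participants in the Sham arm will be informed of their assignment and will restart with active stimulation for 10 weeks". Active participants may continue on maintenance sessions. Concomitant medications are reviewed again at Week 20 (Table 1 and 13.5).

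**The concern.** A treatment first taken after the Week 10 rating cannot have changed that rating. Dropping the participant from a Week 10 comparison therefore removes no contamination and discards a valid blinded score.

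The loss is also unlikely to be random. Whether someone starts another treatment after Week 10 plausibly depends on how they were doing at Week 10 and on the arm they have just been told. The two arms then face different offers: a full active course for former sham participants, maintenance for active participants. If starts differ by arm among non-responders, PP membership depends on both outcome and assignment, and the PP difference moves although the true effect does not.

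The wording has a further literal consequence. Exclusion criterion 5 (12.3) names tDCS, so former sham participants who begin the offered open-label stimulation would have taken a listed treatment during the investigation and would leave PP.

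**Working it through.** **Plan's own figures (22.2).** Inputs: difference 3.2, SDs 7.1 and 7.9, one-sided alpha 0.025, 80% power, 1:1.

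- Average-variance SD = √((7.1² + 7.9²)/2) = 7.51.
- Normal approximation: n per arm = 2 × (1.960 + 0.842)² × 7.51² / 3.2² = 86.5, so 87 per arm, 174 in all.
- Noncentral t: 88 per arm, 176 in all, power 80.2%. At 216, power is 87.6%.
- Attrition: 216 / 0.80 = 270.

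All stated figures reproduce, and none depends on the PP definition.

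**Does the analysis date supply a window?** Under 22.5 the primary endpoint is analysed once all participants have completed Week 10, been withdrawn or passed the window. Assume uniform enrolment over the planned 5 months (5 × 52/12 = 21.7 weeks) and that everyone continues. When the last participant reaches Week 10, (21.7 − 10)/21.7 = 54% have already passed Week 20. The analysis date therefore does not keep open-label events out. It would also make PP membership depend on enrolment date.

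**How many scores could be lost (illustration).** Let r be the assumed proportion starting a listed treatment in each 10-week phase, with all 216 continuing. The number lost only because of events after Week 10 is 216 × r × (1 − r):

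- r = 2%: about 4
- r = 5%: about 10
- r = 10%: about 19

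**Shift in the PP difference (illustration).** From 22.2: SDs 7.1 (active) and 7.9 (sham), true difference 3.2. Assumed: baseline HDRS-17 normal with mean 20 and SD 3, floored at 16; sham mean change -5, -6 or -8; non-responders are those without a reduction above 50%; a fraction p of them is removed.

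For an arm with mean change μ, non-responder share q and non-responder mean change μ_NR:

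PP mean = (μ − p·q·μ_NR) / (1 − p·q)

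With sham change -6 and active change -9.2, simulating 2,000,000 per arm gives q = 0.547 and μ_NR = -4.15 (active), q = 0.694 and μ_NR = -2.06 (sham). Then:

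- Active, p = 20%: (-9.2 + 0.454)/0.8906 = -9.82
- Active, p = 10%: (-9.2 + 0.227)/0.9453 = -9.49
- Active, p = 5%: (-9.2 + 0.114)/0.9727 = -9.34
- Sham, p = 5%: (-6 + 0.071)/0.9653 = -6.14
- Sham, p = 20%: (-6 + 0.286)/0.8612 = -6.64

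| Non-responders removed, active v sham | PP difference | Shift |
|---|---|---|
| 10% v 5% | 3.35 | +0.15 |
| 20% v 5% | 3.68 | +0.48 |
| 5% v 20% | 2.70 | -0.50 |
| 20% v 20% | 3.18 | -0.02 |

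Across sham changes of -5 to -8 the shifts are about +0.12 to +0.16, +0.44 to +0.48 and -0.45 to -0.55 for the first three rows, and below 0.1 in size for equal rates up to 20%.

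For scale, the standard error of the difference with 108 per arm is √(7.1²/108 + 7.9²/108) = 1.02. The shifts are therefore about 0.15 to 0.5 of a standard error.

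**The case against.** **PP has no stated role here.** The primary endpoint uses mITT (22.5), the list in 22.9 uses mITT, and safety uses the As Treated set (22.3.2, 22.14). A reader might infer that PP is the planned check on the primary result, or that the trial's conclusion is at risk. The protocol says neither. This stands and limits the point to a supportive set.

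**A Week 10 window was probably meant.** The same section speaks of a 10-week follow-up period. Applying the bullet literally to open-label tDCS gives a result that no analyst would want. This also stands as a reading of intent, and the SAP may state the limit. But the protocol writes out the PP definition itself, gives windows to other bullets and none to this one.

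**The exposed group is smaller than all non-responders.** Open-label treatment is only offered (11.4), and those who decline finish at Week 10. An active non-responder has little reason to stay. If half decline, a 20% rate among those who stay is 10% overall, which gives the +0.15 row. The listed treatments are also fairly narrow: a changed antidepressant regimen falls under inclusion criterion 4b and only arguably under exclusion criterion 3. A reader might take a larger shift from higher rates: 30% v 5% gives about +0.8. Nothing in the documents supports rates that high.

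**The data are not lost to the trial.** Protocol 15.6 keeps data collected before discontinuation in the analysis, so the Week 10 score remains in mITT. That is correct; the loss is from PP only.

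**Other bullets.** A reader might want the same limit on the major-violation and eligibility bullets. The first is already tied to confounding of assessment during follow-up, and the second most naturally refers to eligibility at entry. No defect is shown in either.

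**Conclusion.** The bullet is wrong as written. For participants who continue to Week 20 it lets events after the endpoint and after unblinding decide whether a valid Week 10 score counts in PP. That such events cannot have affected the Week 10 score follows from timing alone and needs no assumption.

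The size and direction do rest on assumptions, because the documents give no start rates. In the cases considered, the PP difference moves from 3.2 by about +0.15 to +0.5, or by about -0.5 with the arms reversed. With equal rates up to 20% it moves by less than 0.1, and the cost is then mainly lost participants.

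The primary mITT result, alpha and the sample size of 270 are untouched. Participants who end at Week 10 are not affected. This is a wording defect in a supportive set, and it is worth correcting because the correction is so cheap.

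**What to change.** In Protocol 22.3.4, limit this one bullet to listed drugs or treatments first taken between randomization and the Week 10 HDRS-17 rating, before unblinding, for every Week 10 analysis on the PP set. Treatments first taken later, including open-label stimulation, should not affect Week 10 PP membership; describe them only with the Week 20 data. If the SAP repeats the definition, use the same wording there. The major-violation and eligibility bullets need no change.

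Cost: one phrase and a date filter in the PP derivation. There is no new data collection, no burden on participants and no effect on sample size. The PP set may become slightly larger.

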22.4 RANDOMIZATION

After a subject has met all inclusion criteria and none of the exclusion criteria, and creates an account in the Flow app, the subject will be randomized. Randomization will be performed in a 1:1 ratio to the Active and Sham groups. Randomization will be performed using randomly permuted block sizes of 4 and 6 and done independently for the two sites.

22.5 TESTING OF PRIMARY EFFECTIVENESS HYPOTHESES

The primary effectiveness endpoint is the change in adjusted mean group difference in the HDRS-17 scores between 10 weeks and baseline between subjects randomized to the active study device relative to those subjects randomized to sham. The formal statistical hypothesis is as follows:

$$H_{o}: d_{flow} - d_{sham} \leq 0 \\ H_{a}: d_{flow} - d_{sham} > 0$$

Where d_{flow} and d_{sham} are the adjusted mean group difference in HDRS-17 scores in subjects randomized to Active and Sham groups, respectively.

The mITT population will be the analysis population used to analyze the primary effectiveness endpoint. The endpoint will be analyzed when all randomized subjects have completed their 10-week visit, been withdrawn

from the trial or passed the end of their 10-week follow-up visit window. The difference in the group mean differences will be assessed using a mixed model for repeated measures. If the p-value of the difference in the group mean differences is less than one-sided p= 0.025, then the trial declared a success.

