6 STUDY SUMMARY

Study Full Title	Transcranial Direct Current Stimulation in Major Depressive Disorder: A Double-blind, Placebo-controlled, Randomized, Superiority Trial	
Study Sponsor	Flow Neuroscience AB	
Study Number	FL001	
Device Name	Flow FL-100	
Protocol Date	10Jan2023	
STUDY OVERVIEW		
Study Design	Double-blind, placebo-controlled, randomized, superiority, remote.	
Purpose	The purpose of this trial is to investigate the use of the Flow FL-100 device at-home to treat Unipolar Major Depressive Disorder (MDD) in a double-blind RCT.	
Expected Study Duration	10 months	
Evaluation Schedule	Participants will undergo evaluations at the following study visits. Various evaluations regarding depression severity, suicidal ideation will be performed (see Schedule of Evaluations for more detail): • Pre-Treatment Phase - Week -3 - Week -2 - Week -2 - Week -1 • Blinded Phase - Week 0 - Week 1 - Week 4 - Week 7 - Week 10 • Open-Label Phase - Week 20 At week 0, 1, 4, 7, 10, 20, participants will also complete the MADRS-s on their personal smartphone or other device running Android 5.0+ or iPhone Operating System (iOS) 12+.	
ELIGIBILITY CRITERIA		

Intended Participant	Up to 270 participants will be randomized at 2 sites, one located in the United Kingdom and the other in the United
Intended Participant Population	States. The recruitment will be capped to 155 for each of the sites.
	Siles.
	1:1 randomization: Flow FL-100 vs. Sham
	To be eligible to participate in this study, participants must meet all the following criteria:
	1. Be ≥18 years.
	2. Have a diagnosis of Unipolar MDD with a current
	depressive episode as defined by the diagnostic
	criteria in the Diagnostic and statistical manual of
	mental disorders – 5th edition (DSM-V) 3. Have a Hamilton Depression Rating Score (HDRS-17)
	of \geq 16.
	4. For 6 weeks prior to enrollment, are either:
	a. not taking antidepressant medication or:
	b. are taking a stable antidepressant regimen
	with a stable medication source and agree to
	continue the same regimen throughout study participation.
Diagnosis and Inclusion	5. If in psychotherapy, have maintained stable
Criteria	psychotherapy for at least 6 weeks prior to enrollment.
	6. Have access to a stable internet connection through
	which the treatment will be received.
	7. Have access to a smartphone or other device running
	Android 5.0+ or iPhone Operating System (iOS) 12+
	(e.g., reasonably new iPhone/iPad or Android phone),

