22.10 MULTIPLICITY ADJUSTMENT

The secondary endpoints will only be tested if the primary endpoint demonstrates superiority. By pre-specifying the order in which the primary and conditional effectiveness hypotheses are performed, there is no type 1 error inflation and nominal alpha levels may be used on the primary endpoint.

Should the primary endpoint be met, the clinical response endpoint (Endpoint #1 in SAP version 2) will be tested. Should the secondary Endpoint #1 be met, the remaining endpoints will be tested using Hochberg correction for multiplicity. Complete details for multiplicity adjustment are provided in the SAP.

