22.15 INTERIM ANALYSES

An interim analysis testing for futility, sample size re-estimation, and claiming study success with a sample size smaller than the maximum specified is specified. Please see the details in the Adaptive Design Report detailing all elements of this process.

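### Does the single one-sided 0.025 success rule in section 22.5 conflict with the early success claim allowed in section 22.15?

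*Protocol*

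**What the plan says.** Protocol section 22.5 fixes when the primary endpoint is tested: "The endpoint will be analyzed when all randomized subjects have completed their 10-week visit, been withdrawn" or passed the end of the Week 10 window. The rule is then: "If the p-value of the difference in the group mean differences is less than one-sided p= 0.025, then the trial declared a success". The section names no interim look or boundary and does not mention the Adaptive Design Report.

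Protocol section 22.15 reads: "An interim analysis testing for futility, sample size re-estimation, and claiming study success with a sample size smaller than the maximum specified is specified". It continues: "Please see the details in the Adaptive Design Report detailing all elements of this process". It does not refer back to section 22.5.

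Section 22.10 argues from the pre-specified order of the primary and conditional hypotheses that "there is no type 1 error inflation and nominal alpha levels may be used on the primary endpoint". Section 22.2 plans the sample size as a fixed design at one-sided 0.025. The study summary in section 6 gives the size as a ceiling: "Up to 270 participants will be randomized at 2 sites".

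**The concern.** Read alone, section 22.5 spends the whole one-sided 0.025 on one test at the end. Section 22.15 adds a second route to success. If the interim is itself a test that can declare success and the final test still uses 0.025, total error exceeds 0.025 unless something offsets it, such as a binding futility rule. The reason in section 22.10 for using nominal alpha covers the step from primary to secondary endpoints and does not cover repeated looks.

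The stake would be real. Section 24.4 says the data will support a premarket approval application. If the Adaptive Design Report set a final level other than 0.025, the plan would hold two success rules, and a p-value between them would be open to dispute after unblinding.

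**Working it through.** **1. The plan's own figures.** Inputs from section 22.2: difference 3.2, SDs 7.1 and 7.9, one-sided alpha 0.025, power 80%, attrition 20%.
- Common SD = sqrt((7.1² + 7.9²)/2) = 7.511.
- Noncentral t: 87 per arm gives 79.8% power and 88 per arm gives 80.2%, so 176 in total, as stated.
- 108 per arm gives 87.6%, as stated, and 216/0.8 = 270.

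The planning therefore uses 0.025 as the full alpha of a fixed design. It does not show whether that level was later checked against the interim.

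**2. The sections side by side.**
- Section 22.5 ties the analysis to all randomized subjects, whatever their number, and not to 270 of them.
- Section 6 makes 270 an upper limit.
- Section 22.15 speaks of success at less than the maximum.

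These agree if the interim may stop accrual early and one test follows after everyone's Week 10. On that reading section 22.5 applies unchanged to the number reached. The protocol does not say that this is the intended design, but no sentence rules it out.

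**3. If the interim is itself a success test.** No look time or boundary is given in the protocol, so both are assumptions. Take one look at information fraction t, with (Z1, Z2) bivariate normal under the null and correlation sqrt(t).
- O'Brien-Fleming-type interim spend: a1 = 2[1 − Φ(z(0.9875)/sqrt(t))].
- Total error with the final test left at 0.025: 1 − P(Z1 < c1, Z2 < 1.960), where c1 is the interim boundary at level a1.
- Critical difference: SE = sqrt((7.1² + 7.9²)/108) = 1.022, df = 214. At one-sided 0.025 this is 1.971 × 1.022 = 2.015 points.

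| t | interim spend | total error, final at 0.025 | final level that holds 0.025 | shift in critical difference (points) |
|---|---|---|---|---|
| 0.30 | 0.00004 | 0.0250 | 0.0250 | under 0.001 |
| 0.50 | 0.0015 | 0.0255 | 0.0245 | 0.009 |
| 0.54 | 0.0023 | 0.0257 | 0.0243 | 0.013 |
| 0.80 | 0.0122 | 0.0280 | 0.0214 | 0.07 |

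**4. Which t is relevant.** Section 11.1 estimates 5 months of enrolment, about 21.7 weeks, and the outcome is read at 10 weeks. With even accrual, 10/21.7 = 46% of the maximum (0.46 × 270, about 124) is enrolled but unread at a look during accrual. Enrolment therefore closes when about 54% of the outcomes are in. A look at t = 0.80 comes after all 270 are randomized and cannot reduce the number enrolled. The rows up to 0.54 are the ones that matter if the aim is a smaller trial.

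**5. If the interim stops accrual on predicted success.** Simulation under the null, 2 million runs per setting, 1 to 4 looks, predictive-probability thresholds of 90% to 99%, then one test at 0.025:

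| unread share | no futility rule | binding futility at 5% | binding futility at 10% |
|---|---|---|---|
| 46% (protocol timing) | 0.0252–0.0270 | 0.0234–0.0253 | 0.0213–0.0245 |
| 10% | 0.0256–0.0318 | 0.0252–0.0305 | 0.0242–0.0288 |

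Section 22.15 does provide for futility, though the protocol does not say whether it binds.

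**6. The extreme case.** Using 0.025 at both looks gives 0.0447, 0.0416 and 0.0354 at t = 0.3, 0.5 and 0.8. Section 22.5 states 0.025 for one analysis only, so the text does not describe this.

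**The case for a change.** The strongest argument for a change is that this is more than detail left to another document. Section 22.5 writes out a complete, unconditional success rule. Nearby sections defer openly: 22.5.1 and 22.6 to the statistical analysis plan, and 22.10 for full multiplicity details. The success threshold carries no such deferral, although the revision history shows that the reference to the adaptive design was added deliberately in version 8. One sentence would remove any doubt in a trial meant for a marketing application. Accrual slower than estimated would leave fewer participants unread at a look and raise the possible excess, to 0.0318 in the worst setting tried. An increase in sample size after an unblinded look could add to it.

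Part of this stands. Section 22.5 has no pointer to section 22.15, and adding one would be reasonable housekeeping. It does not establish an error. What such a sentence should say about the level depends on the Adaptive Design Report, which section 22.15 says contains all elements of the process. The complaint about section 22.10 falls away, because its sentence already rests on the order of the hypotheses and is correct for that purpose.

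**Conclusion.** The concern does not call for a change. The protocol has a missing cross-reference between two sections of the same chapter; it does not have two success rules shown to conflict. Boundaries, look times and the final level properly sit in the Adaptive Design Report, and an analyst would apply that report together with section 22.5.

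On the protocol's own timing, an assumed O'Brien-Fleming-type look at 54% information gives a total one-sided error of 0.0257 and moves the critical difference by about 0.013 points, against a planned effect of 3.2. Stopping accrual on predicted success gives at most 0.0270 without futility. With binding futility it gives 0.0213 to 0.0253, which is mostly at or below 0.025.

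This rests on even accrual over the estimated 5 months, on the assumed stopping rules, and on no increase in sample size after an unblinded look. If the Adaptive Design Report turned out to set a final level other than 0.025, the question would need to be reopened. Nothing in the protocol indicates that it does.
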